## Research Protocol

The proposed research study is part of a PhD that is taking a phased approach (MRC, 2008) to develop, pilot, and evaluate an exercise referral scheme (ERS) for inactive individuals with health conditions. Study 1 [REF 16/EM/0157] involved the co-development of the intervention in collaboration with a multidisciplinary steering group (e.g. researchers, GP's, commissioners etc.). Study 2 (REF 16/WA/0231) explored the feasibility of the ERS and tested potential outcome measures to inform a subsequent evaluation trial. **Study 3 (this application) will be a pragmatic, quasi-experimental trial to test the effectiveness of the ERS.** The research will be conducted in collaboration with Liverpool NHS Clinical Commissioning Group (CCG) and Liverpool City Council (LCC). **This protocol relates to study 3 only.**

**Formal study title:** “Clinical and cost-effectiveness of a co-developed, evidence-based physical activity referral scheme for the treatment and prevention of health conditions: a pragmatic trial”

**Lay study title:** “Evaluation of a co-developed physical activity referral scheme”

**Aim:** *To test the pragmatic effectiveness and cost-effectiveness of a co-developed, evidence-based physical activity referral scheme, with embedded process evaluation.*

### **Objectives:**

- To investigate the relative effectiveness (for improving cardiorespiratory fitness at 12 weeks) and cost-effectiveness (PA levels at 6 months) of two delivery modes of ERS (1. co-developed physical activity referral scheme; 2. standard ERS)
- To explore who each intervention reaches, patient adherence levels, fidelity of intervention delivery and acceptability of the intervention to patients and staff.

### **Study Design**

A three-arm quasi-experimental trial involving: 1. co-developed physical activity referral scheme (intervention); 2. standard ERS (usual care); and 3. no treatment control. Process evaluation will be embedded to establish reach, adherence, fidelity and acceptability of the intervention and usual care conditions.

## Participants and recruitment

There are two types of participants within the study design:

### 1. Patients

#### *Inclusion Criteria:*

≥18 years old and have a health-related risk factor (e.g. high blood pressure, hyperglycaemia, obesity etc.) or a health condition (diabetes, cardiovascular disease, anxiety, depression etc.) that may be alleviated by increasing current PA levels.

#### *Exclusion Criteria:*

- Uncontrolled health-conditions (Cardiac, metabolic, respiratory etc.) and/or any recent traumatic events (e.g. myocardial infarction).
- Unstable angina or aortic stenosis.
- Severe psychological or neurological conditions.
- Participation in an ERS at any location other than the research centres (at the time of recruitment).

### 2. ERS staff

#### *Inclusion Criteria:*

- Qualified exercise referral practitioner (ERP)
- Involvement in the delivery of the ERS at Centre A (intervention) or Centre B (usual care)

#### *Exclusion Criteria:*

- None

## Recruitment

### ***Intervention and usual care conditions***

Eligible patients will be recruited from Centre A and Centre B (after they have been referred to the ERS by a health professional). Once referred, it is standard protocol that ERS patients visit their chosen *Lifestyles* fitness centre to book an ERS induction with administrative staff. During this initial contact, administrative staff will introduce the study briefly and provide the individual with a summary poster (attached). If the patient is interested, administrative staff will gain verbal consent to pass the patient's contact details to the researcher (NB this is consent for sharing details only, the participant will still have the opportunity to opt out before full research consent is sought). Administrative staff will then provide patients with the participant information sheet to take away and have some time to consider. Patients will be informed that the researcher will contact them within one week to discuss the study and check if they want to take part. Researcher contact details will be provided on the poster and information sheet in case the participant has any questions in the meantime.

For patients who consent to speak to the researcher, the administrative staff will book an ERS induction 2-3 weeks later (to allow time for the patient to undergo baseline testing prior to starting the ERS). The researcher will then contact the patient to arrange a visit to Liverpool John Moores University (LJMU) laboratories for baseline collection of health measures.

Patients who opt out of the study at this stage will continue with the ERS as usual.

#### ***No treatment control condition***

Participants in the no treatment control group will be recruited via posters placed around LJMU, electronic invitations on LJMU research recruitment websites, email communications to LJMU staff and students, and LJMU social media output (see attached documents). Interested participants will contact the researcher for further information, who will e-mail them a full participant information sheet. If the participant then decides to take part the researcher will arrange a date and time to visit LJMU laboratories for baseline collection of health measures.

**Participant blinding.** Due to the nature of the study, it will not be possible to fully blind patients to their study condition (as they will know whether they are signed up to attend an ERS or not) or to blind ERS staff (who will know whether their centre is the intervention or the usual care condition). Patients within the two active conditions (intervention and usual care) will not however be informed whether their centre is the intervention or the usual care condition.

#### **Conditions**

##### ***Intervention (Centre A)***

[figure not shown]
Both the co-developed scheme and standard ERS offer subsidised access to a fitness centre for 12 weeks. However, in addition to this the co-developed intervention (centre A) will offer:

- more physical activity options that include both daily opportunities to increase PA and activities available at the fitness centre;
- more individual progress meetings, during which the GP exercise referral practitioner will provide behaviour change support (Week 0, 4, 8, 12 and 18); and
- more efforts to refer patients to optional additional support from a 'Health Trainer' service qualified to provide advice on multiple health-related behaviours.

These adaptations are in line with the current NICE guidelines as well as a local evaluation study that fed into the development of the scheme. The aim of the co-developed ERS is a person-centred approach to improve overall well-being and quality of life through PA. As the intervention is drawing on an existing scheme, delivered/guided by qualified ERPs, and has been developed by a multidisciplinary stakeholder group involved with the existing scheme, it is deemed that there are no additional risks to the users compared to the existing

scheme in operation. The key aspect of the intervention is that the participant has choice but is supported through the process.

It was found during the pilot study that some patients were referred inappropriately to the ERS who were already active or were seeking subsidised access to certain activities (e.g. swimming) without a need for additional behaviour change support. In an attempt to provide more targeted support, patient eligibility for the ERS will be explored through the patient-centred induction. If it is deemed by both the instructor and patient that the intensive 18-week intervention is not the most appropriate for the patient's needs, alternative options will be offered (see figure 1). Since this study aims to investigate the real-world effectiveness of an ERS that is tailored to patient needs, patients referred to the ERS at Centre A who opt not to take part in the 18-week intervention will remain in the research study (i.e. an intention to treat approach).

**Figure 1.** Co-developed referral scheme that will run at Centre A (intervention centre).

[figure not shown]
*Theoretical underpinning and behaviour change support.* All behaviour change support is underpinned by self-determination theory (SDT, Ryan and Deci, 2000) and aimed at supporting patients to feel autonomously motivated to keep up physical activity in the long-term.

### ***Usual care (Centre B)***

The usual care arm will follow a standard ERS model of 12-week access to a *Lifestyles* fitness centre. Patients referred from a health professional (GP, physiotherapist, nurse etc.) will meet an ERP at the leisure centre for an initial induction (week 1). A personalised exercise intervention will be provided to the patient based on their referral reason/health condition. The patient will have 12 weeks of subsidised access to the gymnasium and group classes. This system is already in place and is considered standard exercise referral care for the local area.

### ***No treatment control***

These participants will receive a lifestyle advice booklet only (provided to all groups at the baseline data collection point).

**Figure 2.** Overview of intervention measure time points for each arm.

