### **Outcome measures**

aAll patient outcome data will be collected at two time-points: pre-intervention (prior to an induction with an ERP) and at Week 12 (post 12-week consultation with an ERP). bAt 6-month follow-up, **questionnaire-based measures and PA levels** (determined by an accelerometer worn for 7 days), **only** will be collected. All data will be collected and analysed by a researcher at LJMU. All outcome measures were piloted in a previous study (REF 16/WA/0231) and were deemed acceptable by patients and demonstrated adequate sensitivity to detect change.

a Collected at Baseline and week 12

b Collected at Baseline, week 12 and 6-month follow-up

a **Cardiorespiratory Fitness.** A sub-maximal VO2 test (Astrand Rhyming test) will be carried out to estimate cardiorespiratory fitness. The Astrand Rhyming test allows you to predict VO2max from work intensity and heart rate. Following a warm-up (unloaded cycling 3-5 minutes at 50-60 rpm) the procedure will begin. Using a Polar Heart Rate Monitor to measure heart rate, the individual will begin cycling at 60 rpm with a workload of 60 watts (female) or 90 watts (male). The participant will then cycle at this workload for 6 minutes. Heart rate will be measured each minute; blood pressure will be measured at each 3-minute period as well as pre- and post-test. If the mean heart rate is between 125 and 170 beats per minute at minute 5 and 6, the test can be terminated. If the mean heart rate is less than 125 beats per minute, the workload will be increased by 30 watts (0.5 kg). If the mean heart rate is less than 125 beats per minute at minute 5 and 6 the test will be continued for a further 3 minutes. This procedure will be repeated until the required heart rate is achieved. The test will be stopped if the participant experiences any adverse effects, their heart rate exceeds recommended max heart rate values for this test, or if the participant wants to stop.

b **Objective PA levels.** Objective PA will be analysed using an accelerometer (ActiGraph software), which will be fitted during baseline testing at LJMU. A baseline 7-day monitoring period will occur before participants engage with the scheme. During the 7-day monitoring period, each participant will complete a diary to record hours of use as well as distinguish between work and leisure hours.

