### **Methods**

A trial- and model-based economic evaluation will be conducted from the public sector perspective, which will include the costs and consequences to the: local authority, NHS and PSS, and local authority leisure centre. Results from all analyses will be reported in the form of an incremental cost-effectiveness ratio. Firstly, a cost-utility analysis will be carried out with the results being presented as cost per quality adjusted life year. Secondly, a cost-effectiveness analysis will be carried out with the results being presented as cost per active participant. Lastly, a cost-consequence analysis will be conducted from a broader perspective, which will highlight relevant public sector and participant costs and consequences. More specifically, the main analysis will be done by exploring the costs and effects over a lifetime horizon, using a decision-analytic model. All costs and effects over the lifetime horizon will be discounted at a rate of 3.5% as recommended in the NICE reference case (NICE, 2017). The 6-month effectiveness data for change in physical activity level, as well as published secondary data sources on change in disease state will be input into the model. The extrapolated analysis will aim to estimate the relative risk of participants being in one of the following six health states 10 years after the intervention: healthy, dead, has had a stroke, has coronary heart disease (CHD), or has type 2 diabetes (T2D). The 10-year duration of effect period is a conservative approach, which has been based on a recently published study (Campbell et al. 2015) that was identified in the systematic review. All

epidemiological data along with additional published secondary data on the life expectancy, health-related quality of life and treatment costs associated with each of the six health states will be input into a Markov Model. Uncertainty will be assessed through deterministic and probability sensitivity analyses.

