### **Patient procedure**

*LJMU lab-based measures.* Written informed consent will be gained prior to the commencement of testing, when patients arrive at LJMU for baseline testing with a researcher. Patients will need to be rested for 20 minutes prior to initiation of the ultrasound techniques. During this period, demographic data will be collected in addition to information about PA levels, mental wellbeing, diet, smoking and alcohol habits, psychological questionnaires and economic-related questions (~30 minutes; see attached Booklet 1 and Booklet 2). Ultrasound measures will then be conducted (FMD and CAR): 25 minutes. A 15ml blood sample will be taken from the antecubital fossa (5 minutes). The participant will then be able to drink and eat, if they wish, prior to completing a sub-maximal fitness test (20 minutes). The patient will then be informed about the accelerometry protocol and given the Actigraph monitor with accompanying diary to be completed over a seven-day period (5 minutes). For the ERS arms, the accelerometer and accompanying diary will be returned to the ERP when the patient attends their referral induction at Centre A or Centre B to begin their programme. The control group participants will return the monitors to LJMU in person or by pre-paid mail. The expected period to complete baseline testing is ~90-120-minutes.

Lab based testing will be repeated at week 12 as per the protocol for baseline data collection described above. At 6 months from baseline, participants will be sent (by mail) a questionnaire pack (booklet 2) and an activity monitor. These will be returned via pre-paid mail or as otherwise organised with the researcher.

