### **Protocol for incidental disclosures or abnormal test results**

*Disclosure of unhealthy lifestyle* – Whilst it is not deemed appropriate for researchers to pass on lifestyle information disclosed in confidence, or to provide individual advice, it is recognised that the research team have a responsibility to provide evidence-based information to allow patients to make informed decisions about their health. Therefore, after completing their baseline assessments at LJMU participants will each be given a simple information sheet that outlines the recommended guidance on PA and diet as well as risks associated with smoking and alcohol. On the sheet participants will be signposted to relevant government

websites for further information and will be advised to contact their GP if they have any concerns about their own lifestyle.

*Abnormal test results.*

The laboratory-based testing is not diagnostic in nature and is therefore not likely to find anything alarming. However, if any abnormal blood results (analysed following week 12 testing) are identified, the researcher will write to the individual participant and ask them to see their GP. Refer to attached patient letter.

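### The 7-day baseline accelerometer wear follows the study's physical activity advice in every arm, so baseline objective activity is a post-advice value

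*Combined protocol and SAP*

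**What the plan says.** Four sections of the combined protocol and SAP bear on the order of events at baseline.

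- **Conditions, No treatment control:** "These participants will receive a lifestyle advice booklet only (provided to all groups at the baseline data collection point".
- **Protocol for incidental disclosures or abnormal test results:** "after completing their baseline assessments at LJMU participants will each be given a simple information sheet that outlines the recommended guidance on PA and diet".
- **Outcome measures, Objective PA levels:** the accelerometer is a device "which will be fitted during baseline testing at LJMU", and "A baseline 7-day monitoring period will occur before participants engage with the scheme".
- **Patient procedure:** after questionnaires, ultrasound, blood sample and fitness test, the participant is "given the Actigraph monitor with accompanying diary to be completed over a seven-day period". On the visit's length: "The expected period to complete baseline testing is ~90-120-minutes". Referral-scheme patients hand the monitor back to the exercise referral practitioner at induction. Controls return it to the university in person or by post.

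The economic Methods section takes as a model input "The 6-month effectiveness data for change in physical activity level" and does not name the instrument. The Analyses section treats baseline as a level of time in the mixed model and also lists baseline values among the covariates.

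**The concern.** A baseline should describe participants before the study does anything meant to change the outcome. The protocol guards the accelerometer baseline against contact with the scheme, but not against the study's own activity guidance. That guidance is also the only thing the control arm receives, so for controls the wear week falls after their allocated condition has been delivered.

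The two activity baselines also fall on opposite sides of the advice. The short IPAQ is a seven-day recall completed during the visit, so it describes the week before. The accelerometer describes the week after. Changes on the two measures would then start from different reference points.

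What is at stake is change in accelerometer activity within each arm and, under a further condition, the contrast of the referral arms with the controls. No pre-advice wear days will exist, so the order cannot be corrected once data are collected.

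**Working it through.** The plan states no figure on this point, so the check is of sequence, followed by simple algebra.

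**1. Timeline (Patient procedure; Outcome measures; No treatment control; incidental disclosures)**

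| Event | When |
|---|---|
| Questionnaires including IPAQ, ultrasound, blood, fitness test | Day 0, laboratory visit |
| Monitor issued (last listed item) | Day 0 |
| Activity guidance handed over | Day 0, after the laboratory assessments |
| Baseline wear | The following 7 days |
| Monitor returned | Induction (referral arms); in person or by post (controls) |

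The moment at which the sheet changes hands relative to the monitor is not given, but it does not matter. A visit of 90 to 120 minutes cannot contain a seven-day wear, so either order puts the wear week after the advice. No later baseline contact at the university is described at which the advice could be given instead. Pre-advice wear days: 0 of 7, for all 70 + 70 + 30 = 170 planned participants.

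**2. Effect on within-arm change**

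Let s be the rise in activity during the wear week caused by the advice. Then observed change = follow-up − (true baseline + s) = true change − s. This holds whether or not the response lasts to follow-up.

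**3. Effect on between-arm contrasts**

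For simple change scores, the bias in arm A minus arm B is −(s_A − s_B). With baseline as a covariate and slope b, it is −b(s_A − s_B). All values below are assumed, in min/week, with true changes of 20 (intervention), 10 (usual care) and 5 (control):

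| Shift: intervention, usual care, control | Observed changes | Intervention − usual care | Intervention − control |
|---|---|---|---|
| 0, 0, 0 | 20, 10, 5 | 10 | 15 |
| 5, 5, 5 | 15, 5, 0 | 10 | 15 |
| 2, 2, 5 | 18, 8, 0 | 10 | 18 |
| 0, 0, 5 | 20, 10, 0 | 10 | 20 |

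An equal shift lowers every arm's change by 5 and leaves both contrasts alone. A shift in controls alone moves intervention minus control from 15 to 20, a bias of 5 on change scores. With baseline adjustment the bias is b × 5, which lies between 0 and 5 for a slope between 0 and 1.

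**4. Scale**

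The documents give no response to the advice. If it were 2 to 5 min/day, within-arm change would be understated by 2 × 7 = 14 to 5 × 7 = 35 min/week. That range is only the assumption multiplied by seven.

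**The case against.** The strongest case on the other side has five parts.

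**The order is inferred.** No sentence says the advice precedes the wear, the figure showing measurement time points is not available, and the control arm's booklet is never expressly identified with the information sheet. This is fair, but both items are tied to baseline and go to everyone. Stretching the laboratory assessments to include wear at home does not fit monitors that are returned at a leisure centre or by post.

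**The main comparisons are largely untouched.** This stands. Cardiorespiratory fitness at 12 weeks has its baseline test at the visit, before the sheet. All arms get the same advice at the same point, so a common response cancels from every between-arm contrast and from the activity increment in the incremental cost-effectiveness ratios.

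**The economic consequence is conditional.** A reader might infer that the lifetime model is biased. The Methods section does not say whether its activity change comes from the accelerometer or from the IPAQ, which is also collected at baseline and 6 months. Nor does it say that cost per active participant uses a baseline at all.

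**The sheet's effect is not an objective.** A reader might also object that the control arm cannot show what its only treatment does. The Objectives do not ask that. The sheet is background common to all arms, and a post-advice baseline can be defended for estimating what the scheme adds to it.

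**Moving the sheet does not make the arms alike.** Referral patients have already been sent for exercise by a health professional, while controls answer university advertising. That difference would remain. What the change removes is a further possible difference created by the study itself.

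**Conclusion.** The point holds in limited form. As written, baseline accelerometer activity is a post-advice measurement in all three arms, and baseline fitness and IPAQ are not. If the advice raises activity, within-arm change in accelerometer activity is understated by the size of that response. A between-arm contrast is biased only by the difference in response, multiplied by the baseline slope where baseline is adjusted for. The contrast most exposed is referral arms against controls, because the trial is not randomised and the two groups are recruited by different routes. Intervention against usual care is less exposed, since both consist of referred patients awaiting induction.

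The documents support no numerical size. The 14 to 35 min/week above should not be quoted as an estimate, and nothing in the documents shows that the response does differ by arm. The conclusion rests on reading the monitor and the advice as belonging to one visit, and its direction on the advice increasing activity. It is a cheap improvement to one measure, not a threat to the fitness result.

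**What to change.** In No treatment control, Patient procedure, and Protocol for incidental disclosures or abnormal test results, state that the booklet or information sheet goes to all arms only after the 7-day baseline wear has ended. Posting it on a fixed day after the visit, whether or not the monitor has come back, keeps the timing the same across arms and independent of compliance. Say whether the booklet and the sheet are the same item.

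In Outcome measures, state that baseline accelerometer activity precedes the study's own advice sheet. Do not call it free of advice altogether, since referred patients may have had some before enrolment. In the economic Methods section, name the instrument that supplies the activity input.

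The cost is a few lines of protocol text and one mailing per participant; the protocol already uses the post for its 6-month packs. The downside is that the information reaches participants about one to two weeks later. If that delay is not acceptable, the minimum is to state that baseline accelerometer activity is a post-advice value and to interpret within-arm change accordingly.
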